## 2. Study Objectives

### 2.1 Study 1

Study 1 will test the central hypothesis that high dose isoflurane anesthesia inducing EEG burst suppression (High ISO/BS+) is a more effective intervention for severe depression when compared to a low dose isoflurane anesthesia that does not induce EEG burst suppression (Low ISO/BS-). The proposed study is a randomized, double-blind trial that will evaluate 30 actively depressed participants with moderate to severe depression. Depression outcomes will be compared between two groups of participants (n=15 per group) who have received 10 treatment applications over a period of three weeks of either High ISO/BS+ or Low ISO/BS-.

Aim 1. To determine whether High ISO/BS+ is more effective than Low ISO/BS- in producing either a treatment response (defined as 50% reduction in depression scores) or full remission of depressive symptoms. We hypothesize that significantly more depressed participants randomized to receive 10 treatments of High ISO/BS+ compared to Low ISO/BS- will show a positive treatment response or full remission by treatment end. Based on the STAR\*D Trial, a responder is a participant showing 50% reduction in depression score and full remission is defined as a score of 0-10 on the HRSD-24 scale and score of 0-5 on the QIDS-SR16.

Aim 2. Preliminary data on neural and immune pathways that are differentially affected by the 2 treatments and associated with antidepressant effects will be explored by comparing changes from pre-treatment to post-treatment in full transcriptome leukocyte gene expression (using the RNA Seq method).

Aim 3. To measure the central neurochemical effects of isoflurane treatment, we will quantify neurotransmitter levels (GABA and glutamate) using magnetic resonance spectroscopy.

### 2.2 Pilot Study 2

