### **4.1 Inclusion Criteria**

We will recruit depressed patients referred to the University Neuropsychiatric Institute for an ECT consult.

- Diagnosis of Major Depressive Disorder (MDD) or bipolar Disorder (I or II, most recent episode must be depression)
- Failed at least 2 anti-depressant treatments and no ECT in past 6 months
- Age between 18-55 years
- BMI < 40
- Hamilton Rating Scale for Depression (HSRD) score > 18
- Quick Inventory of Depression Scale (QIDS) score > 10.

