## **5.3 Clinical Assessments**

**5.3.1 Primary Response Assessments:** The primary outcome measure is change in depressive symptoms assessed by the Hamilton Rating Scale for Depression (HRSD-24), which is the most widely used method of evaluating the effectiveness of treatments to relieve depression. HRSD-24 will be administered as part of a clinical interview by blinded investigators prior to beginning the treatments, then repeated before treatment #6 and at the end of treatments.

**5.3.2 Secondary Response Assessments to be acquired before each treatment:** Also as standard of care for patients receiving ECT, the participant will fill out the Quick Inventory of Depressive Symptomatology (QIDS-SR) which is a patient self-report measure of depressive symptoms prior to each treatment session. QIDS scores will also be used as a safety measure. If 2 consecutive QIDS scores indicate worsening of depressive symptoms, below pre-treatment values, the study participant will meet with one of the study Psychiatrists to discuss treatment alternatives. The Montreal Cognitive Assessment (MoCA), Generalized Anxiety Disorder scale (GAD-7), and Work and Social Adjustment Scale (WSAS) will be administered prior to beginning the treatments, then repeated before treatment #6, and 48-72 hours post treatment #10.

**5.3.3 Follow-up Assessments to be acquired monthly for up to 6-months post treatment period:** Follow-up assessments will include QIDS-SR, WSAS, and an opened ended question about the participant's experience during the study. Follow-up assessments will be administered over the phone or by email with a link to an electronic survey housed on REDCap (a secure online database). A voicemail may be left (with prior permission) regarding the follow-up assessments.

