### **6.3 Safety and Efficacy Monitoring**

All serious adverse events will be reported within 5 days to the Data and Safety Monitoring Board (DSMB) and IRB by the Principal Investigator or study coordinators. These would include life-threatening cardiac arrhythmias, respiratory arrest, myocardial infarction, stroke, and death. Moderate adverse events including worsening of depressive symptoms will be reported to the DSMB. An interim data analysis will be performed at the midpoint of this pilot investigation, after data is obtained from 5 participants in each of the treatment conditions. The study will be terminated if significantly greater negative outcomes are associated with either isoflurane treatment or propofol treatment.

Prior to each treatment, participants will fill out the QIDS-SR. HRSD-24 will be obtained at baseline, before treatment 6, and after treatment 10. All participants will be assessed before the 6th treatment. If participants in Low ISO/BS- or propofol treatment groups show clinical deterioration (defined by 2 consecutive QIDS scores below baseline OR a decrease in HRSD-24 before the 6th treatment), they will be offered treatment at the 80% burst suppression level (High ISO/BS+) as it has proven effective in reducing depression or ECT as the standard of care treatment. Participants in High ISO/BS+ treatment who show clinical deterioration, as defined above, will be offered ECT. All serious adverse events will be reported within 5 days to the DSMB by the Principal Investigator or study coordinators. The DSMB will also be notified within 10 business days if a study participant is showing signs of clinical deterioration (defined as 2 consecutive QIDS scores below baseline OR HRSD-24 below baseline). Progress reports will be submitted every 6 months. If a participant has a serious reaction to anesthesia, they will be withdrawn from the study.

As exploratory biomarkers, we will evaluate whether quantitative cortical EEG changes early in treatment (obtained from dual lead BIS data in each treatment session) are associated with subsequent remission in depressive symptoms.

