## **7. Statistical Considerations**

Statistical analyses will employ a statistical mediation model framework. Any participant missing necessary information will be excluded from statistical analysis. Only participants with usable data will be included in the analyses. If the original statistical plan becomes infeasible, the original plan and the modifications made will be reported.

**7.1 Aim 1.** To determine if significantly more depressed participants randomized to receive 10 treatments of High ISO/BS+ will show a positive treatment response (defined as 50% reduction in depression scores) or achieve full remission of symptoms by treatment end compared to those in the Low ISO/BS-group, odds of treatment response and remission will be compared between groups using logistic regression analysis with positive response at treatment end (yes/no) as the dependent variable, and treatment group (High ISO/BS+ vs Low ISO/BS-) as the independent variable. Positive treatment response is defined as 50% reduction in depression scores, and remission will be defined as a score of 0-10 on the HRSD-24 scale.

Covariates will include baseline depression severity and possibly other baseline demographic and clinical measures as needed.

**7.2 Aims 2 and 5.** Using RNA SEQ methods, we will also explore whether participants who respond to treatment show blood-based changes in gene expression of neural and immune pathways previously associated with refractory depression or suicidality by our group or others. A t-test or non-parametric Wilcoxon test will be used, as appropriate. Change from baseline to end of treatment in gene expression levels will be correlated with change from baseline to end of treatment in HRSD-24.

**7.3 Aim 4.** In the open-label trial of propofol, initial evidence of efficacy will be defined by the percent of participants who show at least a 20% reduction in both HRSD and QIDS scores (initial improvement, as employed in the STAR D investigation) and who are propofol/BS+ responders (defined as 50% or more reduction in both HRSD-24 and QIDS scores). Secondary evidence of efficacy will be defined by comparing the percent of participants who are responders to propofol/BS+ vs. to the Low ISO/BS- control condition in the randomized trial.

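### The score criteria for clinical deterioration in sections 6.3 and 5.3.2 point the wrong way: as written, a falling (better) score triggers rescue and DSMB notice, and a rising one does not

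*Combined protocol and SAP*

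**What the plan says.** Three rules use depression scores to detect a participant who is getting worse.

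- **Rescue offer (section 6.3).** Low ISO/BS- or propofol participants who "show clinical deterioration (defined by 2 consecutive QIDS scores below baseline OR a decrease in HRSD-24 before the" sixth treatment are offered High ISO/BS+ or ECT. High ISO/BS+ participants who meet the same definition are offered ECT.
- **DSMB notice (section 6.3).** The DSMB is told within 10 business days of signs of clinical deterioration, here "defined as 2 consecutive QIDS scores below baseline OR HRSD-24 below baseline". No time limit is attached to either part.
- **Psychiatrist meeting (section 5.3.2).** The QIDS safety rule begins "If 2 consecutive QIDS scores indicate worsening of depressive symptoms, below pre-treatment values" and leads to a discussion of treatment alternatives. It uses the QIDS only.

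The rest of the document fixes the direction of the two scales. Entry requires "Hamilton Rating Scale for Depression (HSRD) score > 18" and "Quick Inventory of Depression Scale (QIDS) score > 10" (section 4.1). Under Aim 1 in section 2.1, "a responder is a participant showing 50% reduction in depression score". In section 7.1, "remission will be defined as a score of 0-10 on the HRSD-24 scale", and section 2.1 adds a QIDS-SR16 range of 0-5. Section 7.3 treats "at least a 20% reduction in both HRSD and QIDS scores (initial improvement") as early evidence that propofol works.

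**The concern.** A score below baseline is what the trial calls improvement everywhere except in these three rules. The wording in 6.3 is hard to excuse as loose: a decrease in HRSD-24 names a numerical direction, and it is the wrong one.

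If site staff program, follow or audit the rule as written, four things follow:

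- A participant whose HRSD-24 and QIDS both rise triggers neither the rescue offer nor the 10-day notice. These are patients who have already failed at least two antidepressant treatments.
- Improving High ISO/BS+ participants are offered ECT, which section 3 describes as carrying significant cognitive adverse effects.
- The DSMB receives notices about improvement, labelled as deterioration.
- Improving Low ISO/BS- participants are offered the experimental treatment before the treatment-end outcome. With 15 per arm, a few acceptances would matter to the Aim 1 comparison.

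**Working it through.** The plan gives no figure to reproduce here. The check compares the direction of each rule with the direction of the scales, then asks who meets each rule.

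**Inputs**

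| Item | Value | Place |
|---|---|---|
| HRSD entry | > 18, so at least 19 in whole points | 4.1 |
| QIDS entry | > 10, so at least 11 in whole points | 4.1 |
| Response | 50% reduction | 2.1, 7.1 |
| Remission | HRSD-24 at most 10; QIDS at most 5 | 2.1, 7.1 |
| Initial improvement | at least 20% reduction | 7.3 |
| HRSD-24 timing | baseline, before treatment 6, end of treatment | 5.3.1, 6.3 |
| QIDS timing | before every treatment | 5.3.2, 6.3 |

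Write *b* for baseline and *s* for the later score. I assume whole-number scores, that the HRSD entry criterion refers to the HRSD-24 (section 4.5 uses the HRSD-24 to verify eligibility), and that the baseline score used by the rules also meets the entry threshold.

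**Direction.** Entry needs a high score. Response, initial improvement and remission need a lower one. So *s* < *b* is better and *s* > *b* is worse on both scales. The document defines no reversed or change score that would alter this. All three rules in 6.3 and 5.3.2 use *s* < *b*.

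**Who has *s* < *b*?**

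- HRSD-24 response: *s* ≤ 0.5*b*. At *b* = 19, 0.5 × 19 = 9.5, so *s* ≤ 9 and the fall is at least 19 − 9 = 10.
- HRSD-24 remission: *s* ≤ 10. At *b* = 19 the fall is at least 19 − 10 = 9. The smallest fall for response or remission is therefore 9.
- QIDS response: at *b* = 11, 0.5 × 11 = 5.5, so *s* ≤ 5. Remission also needs *s* ≤ 5. The smallest fall is 11 − 5 = 6.
- 20% improvement: at *b* = 19, 0.2 × 19 = 3.8, a fall of at least 4 on the HRSD-24. At *b* = 11, 0.2 × 11 = 2.2, a fall of at least 3 on the QIDS.

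Larger baselines do not reduce these minima. The documents do not give the scale maxima, so I enumerated all whole-number pairs under assumed maxima of 40, 60 and 75 for the HRSD and 21 and 27 for the QIDS. The result was the same each time:

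| State at the assessment | Share with *s* < *b* (as written) | Share with *s* > *b* (reversed) |
|---|---|---|
| Responder or remitter | 100% | 0% |
| At least 20% improved | 100% | 0% |
| Any rise | 0% | 100% |

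The table describes one scale at one assessment. For the rescue rule, the relevant HRSD-24 assessment is the one before treatment 6. The DSMB notice has no time limit, so as written it also covers every HRSD-24 responder or remitter at treatment end.

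**Two cases.** HRSD-24 from 30 to 14 before treatment 6 is a fall of (30 − 14)/30 = 53%. That is large enough to be a response, and it is deterioration under 6.3. HRSD-24 from 30 to 40 is a rise of (40 − 30)/30 = 33%, and it does not meet the HRSD-24 criterion.

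**QIDS part.** No minimum change is set, and the baseline QIDS is taken just before treatment 1. A one-point fall seen before treatments 2 and 3 is already two consecutive scores below baseline.

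**Illustration only.** If the 75% HRSD response rate of the earlier open-label study (8 patients, section 3) held in the High ISO/BS+ arm, 0.75 × 15 = 11.25. About 11 of 15 participants would then be reportable to the DSMB as deteriorating because they had responded.

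**The case against.** The strongest reply is that nobody would apply the rule this way. Both definitions in 6.3 are labelled clinical deterioration, and below baseline plausibly stands for worse than baseline. Section 5.3.2 requires scores that indicate worsening, so that sentence contradicts itself and an improving participant would not meet it. Section 6.3 separately sends worsening symptoms to the DSMB as a moderate adverse event, and section 9.1 has study physicians act if symptoms get worse. The HRSD-24 interviewers are experienced clinicians. All of this stands, and it makes the harm conditional. It does not supply a correct score rule, because none of these passages gives a threshold in the right direction. Staff who acted sensibly would be departing from the written definition.

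Three narrower points also have force:

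- The 100% and 0% figures belong to one scale at one assessment. An eventual responder may not have improved before treatment 6, and under a corrected rule could be flagged for an early rise.
- The two parts are joined by OR, so a participant whose HRSD-24 rises could still be flagged by two lower QIDS scores. Only someone worsening on both scales is certain to be missed.
- The effect on Aim 1 needs improving controls to accept the offer, and the plan does not say how they would be analysed. If kept as assigned, their outcome includes the experimental treatment. If withdrawn, data collection stops (Subject Withdrawal and Study Completion) and section 7 excludes those with missing information, so the control arm loses improvers. The comparison is distorted either way, but the net direction and size cannot be derived from the documents.

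A correctly directed rule would also allow crossover, though for worsening controls. How crossover is analysed is a separate question that this correction does not settle.

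**Conclusion.** The concern holds. Both definitions in 6.3 are reversed, and 5.3.2 carries the same wrong score direction inside a sentence that otherwise speaks of worsening. The reversal is complete on either scale at a given assessment: everyone who has responded, remitted or improved by 20% is on the deterioration side of baseline, and no one whose score has risen is. This follows from the protocol's own thresholds and does not depend on the assumed scale maxima.

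The practical harm depends on literal use, and the intent is very probably the opposite. I would still require the correction, because this wording is the only score-based trigger for the rescue offer and the 10-day DSMB notice, and following it exactly would be unsafe.

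**What to change.** Change the wording at three places:

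1. **Section 6.3, rescue offer:** two consecutive QIDS scores *above* baseline, or an *increase* in HRSD-24 from baseline at the assessment before treatment 6.
2. **Section 6.3, DSMB notice:** two consecutive QIDS scores *above* baseline, or an HRSD-24 *above* baseline.
3. **Section 5.3.2:** replace *below* with *above* in the comparison with pre-treatment values.

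With these changes, an HRSD-24 responder is no longer flagged by that scale at that assessment, and any rise is flagged. Whether a minimum rise should be required, so that a one-point change does not trigger the rule, is for the sponsor's clinicians and the DSMB to decide.

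The cost is a wording amendment to two sections, with no new data, visits or participants.

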#### **4.5 Study Visits**

**Screening:** Patients who have been referred or have volunteered for the study will be screened in person or by phone to verify that inclusion and exclusion criteria have been met.

**Consent procedures:** Each patient will be given a full verbal explanation of the study procedures, including risks, benefits, and alternatives, and will be given a copy of the approved written consent form. The patients will be given the opportunity to review the consent form and to discuss any questions or concerns with their own psychiatrist, our study investigators, or others if necessary prior to beginning study treatment procedures.

**Baseline:** Prior to the first treatment, depression severity will be assessed via a psychiatric interview, including completion of the HRSD-24 and MoCA, which will also verify inclusion and exclusion criteria. Immediately before treatment 1, the participant will complete the QIDS and a blood sample will be obtained from the IV line.

**Randomization (Study 1 only):** Participants who meet study criteria will be randomly assigned in blocks of 4 to either high or low dose isoflurane (High ISO/BS+ vs. Low ISO/BS-). We anticipate up to 15 participants in each arm; this sample size was defined by our prior study in which 8 participants were adequate to show significant antidepressant effects.

**Leukocyte Gene Expression:** Although our study is designed with EEG burst suppression as our primary target mechanism, we acknowledge that its effects must be mediated via specific neural pathways. Thus, we will explore possible neural and immune pathways associated with the antidepressant effects of deep anesthesia. Changes in full transcriptome leukocyte gene expression from pre- to post-treatment will be assessed from blood samples drawn before the first treatment and within 48 hours of the final (10th) treatment. In particular, we will examine the possible role of GABA-ergic and ATP-responsive ion channel pathways as well as other putative depression- or suicidality-linked neuroimmune pathways. We will also evaluate other ATP-responsive ion channels (purinergic, acid sensing and transient vanilloid receptor) or other

genes including IL-10 and other cytokines, SAT1, PTEN, MARCKS and MAP3K3 previously associated with refractory depression or suicidality by our group and others. [42918](#)

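### The deterioration definitions in 5.3.2 and 6.3 set no minimum size and differ from one another, so a participant with no true change would meet the 6.3 offer rule by chance more often than not

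*Combined protocol and SAP*

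**What the plan says.** Three statements in the combined protocol and SAP bear on this.

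- **5.3.2, QIDS safety rule.** "If 2 consecutive QIDS scores indicate worsening of depressive symptoms, below pre-treatment values, the study participant will meet with one of the study Psychiatrists" to talk over alternatives. It uses QIDS only.
- **6.3, offer rule.** Deterioration means "2 consecutive QIDS scores below baseline OR a decrease in HRSD-24 before the" 6th treatment. Low ISO/BS- and propofol participants who meet it are offered High ISO/BS+ or ECT. High ISO/BS+ participants who meet it are offered ECT.
- **6.3, DSMB notice rule.** The DSMB is told within 10 business days of deterioration, here "defined as 2 consecutive QIDS scores below baseline OR HRSD-24 below baseline". No time limit is attached to the HRSD-24 part.

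On timing, 4.5 says "Immediately before treatment 1, the participant will complete the QIDS", and 6.3 says "Prior to each treatment, participants will fill out the QIDS-SR" and "HRSD-24 will be obtained at baseline, before treatment 6, and after treatment 10".

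None of the three statements gives a number of points, a percentage or a reliable-change limit. The 20% and 50% limits in 7.3 concern improvement and response in Aim 4, not deterioration.

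**The concern.** With no minimum size, a difference of one point from one baseline reading counts. The QIDS is read again up to nine times, any adjacent pair will do, and the HRSD-24 comparison is joined to it by OR. A rule built this way is met often by ordinary fluctuation around an unchanged level, so its label does not describe what it selects.

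The consequence makes this a matter for the analysis. For a Low ISO/BS- participant the offer is the other randomised condition, or ECT, and it can come before the treatment-end assessment on which Aim 1 rests. There are 15 participants per arm. Section 7 does not say how a participant who accepts the offer is analysed, and it excludes those with missing information. The DSMB also cannot interpret a deterioration notice without knowing how often an unchanged participant would generate one.

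**Working it through.** The plan gives no false-trigger rate, so there is no figure to reproduce.

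**Inputs from the documents.** There is one QIDS baseline, before treatment 1. There are then 5 later QIDS scores up to treatment 6, or 9 up to treatment 10. One HRSD-24 comparison falls before treatment 6. Each arm has 15 participants.

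**Step 1: exact case, no SD needed.** Take no true change, continuous scores and independent errors. Given the baseline value, each later QIDS score falls on the triggering side with some probability p, and over participants p is uniform on (0,1). The chance that k of n scores trigger with no two adjacent is C(n-k+1, k) p^k (1-p)^(n-k). Averaging over p gives

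P(no run of 2) = sum over k of C(n-k+1, k) / [(n+1) C(n, k)].

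- n = 5: 1/6 + 5/30 + 6/60 + 1/60 = 0.450. The QIDS part triggers in 55.0%.
- n = 9: 1/10 + 9/90 + 28/360 + 35/840 + 15/1260 + 1/1260 = 0.332. The QIDS part triggers in 66.8%.

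The HRSD-24 part triggers with probability 1/2. So either part triggers in 1 - 0.450 × 0.5 = 77.5% (n = 5) or 1 - 0.332 × 0.5 = 83.4% (n = 9).

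**Step 2: whole-number scores.** Ties do not trigger, which lowers the rates. For HRSD-24 with SD 3, the difference has SD 3 × √2 = 4.24, a tie has probability about 1/(4.24 × √(2π)) = 0.094, and the part triggers in (1 - 0.094)/2 = 45%. The rest was simulated. Assumptions, none of them in the documents: QIDS within-person SD 1-2.5, HRSD-24 SD 3, session-to-session QIDS error correlation 0-0.8, and correlation between QIDS and HRSD-24 errors 0-0.6.

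| QIDS window | QIDS part | HRSD-24 part | Either, QIDS-HRSD error correlation 0 | Either, correlation 0.6 |
|---|---|---|---|---|
| To treatment 6 | 37-51% | 45% | 65-73% | 59-66% |
| To treatment 10 | 50-65% | 45% | 73-81% | 66-74% |

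The overall ranges are 59-73% and 66-81%. In 15 unchanged participants that is 15 × 0.59 to 15 × 0.73, about 9 to 11, or 15 × 0.66 to 15 × 0.81, about 10 to 12.

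**Step 3: wider assumptions.** With QIDS SD up to 3 and HRSD-24 SD 1.5-4, whole-number scores give 56-82% over both windows. Continuous scores with correlated errors give 69-86%. Selecting on the 4.1 entry thresholds (QIDS SD 2, HRSD-24 SD 3, QIDS-HRSD error correlation 0.3) gives 70-79% if a falling score counts and 65-74% if a rising score counts, so regression to the mean does not remove the problem.

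**Step 4: true improvement, with worsening counted.** QIDS SD 2, HRSD-24 SD 3, improvement reached gradually by treatment 6, QIDS and HRSD-24 errors independent, session correlation 0-0.8:

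- 2 QIDS and 4 HRSD-24 points better: either part triggers in about 35-41%.
- 4 QIDS and 6 HRSD-24 points better: about 15-23%.

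Allowing for shared QIDS and HRSD-24 error takes the lower ends to about 30% and 13%.

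**The case against.** The strongest reply is that zero true change is a special case. The nearest figure in the Background, from a low-dose sevoflurane pilot with 4 treatments, is a 24% reduction in symptoms. On the lowest qualifying HRSD score of 19 that is 0.24 × 19 = 4.6 points, between the two improvement scenarios above. The agent differs and the Background does not name the scale, but the point stands: the high rates describe unchanged participants, and how many of those there will be is unknown.

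The window is also ambiguous. If the words about the 6th treatment govern both parts of the offer rule, only the 59-73% range applies. A reader might infer a general rate of four fifths, but on whole-number scores that needs the QIDS part to run to treatment 10 and nearly independent errors on the two scales.

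A reader might infer that the rule removes the contrast Aim 1 needs. The documents do not show that. They describe an offer with unknown uptake, High ISO/BS+ participants who meet the definition are offered ECT, and 7.1 compares by treatment group. Dilution is possible; its size cannot be computed. A reader might also infer that DSMB notices would be mostly noise. That needs the share who truly worsen, which the documents do not give.

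The conflict between 5.3.2 and 6.3 is partial: the meeting with a psychiatrist could be where the 6.3 offer is made. The difference in scales remains, as does the difference in time window between the two 6.3 rules.

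Finally, a very sensitive safety trigger can be a deliberate clinical choice. That is fair, but the plan neither says so nor shows what it costs in false triggers.

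**Conclusion.** The point holds as a wording and design weakness. Three definitions of worsening or deterioration give no minimum size and do not match. Under no true change the 6.3 offer rule is met by chance in more than half of participants throughout the assumptions examined: 59-73% through treatment 6 and 66-81% if the QIDS part runs to treatment 10. These are model figures resting on assumed SDs and correlations. They fall well below half if participants improve and worsening is what is counted. The supported consequence is that unchanged Low ISO/BS- participants would often qualify for an offer of High ISO/BS+ or ECT before the Aim 1 endpoint, which could dilute the randomised comparison.

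Direction is a related problem in the same sentences. Section 2.1 treats a falling score as response, yet 6.3 describes deterioration as scores below baseline or a decrease. At zero change the chance rate is similar in either direction. With true improvement the literal reading triggers more often and the worsening reading less often.

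**What to change.** Reconcile 5.3.2 and the two statements in 6.3, so that one definition with the same scales, time window and direction stands in all three places. State in it the size of change the study psychiatrists intend; if any one-point difference is intended, say so. Make clear how the 5.3.2 meeting relates to the 6.3 offer. Before finalising, simulate the chosen definition under no change and under modest improvement, and record the false-trigger rates beside it. Deal with the direction wording in the same edit. This review proposes no size and no clinical response.

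The cost is protocol wording and a short simulation. If a size above one point is chosen, very small changes would produce fewer notices; whether that is acceptable is for the study psychiatrists to judge.
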